Percentage of subjects who have died (all- cause and CV related) will be summarized descriptively by treatment.

All recorded adverse events will be listed and tabulated by system organ class, preferred term and treatment. Vital signs and clinical laboratory test results will be listed and summarized by treatment. Any significant physical examination findings, and clinical laboratory results will be listed. ECG readings will be evaluated by the investigator and abnormalities, if present, will be listed.

Percentage of subjects with discontinuations due to symptomatic hypotension, as well as percentage of subjects with down-titrations or interruptions or discontinuations as a result of hypotension, either protocol specified clinically relevant hypotension, or asymptomatic decreases will be summarized descriptively by treatment.

In addition, the final infusion dose at the completion of 48 hours infusion will be summarized descriptively by treatment. The subjects who discontinued prematurely from infusion would be counted as having a final infusion dose of 0 µg/kg/min.

Cardiodynamic ECG assessment (Subset of Subjects in Part II Cohort 2 only):

The analysis will be based on exposure-response modeling of the relationship between plasma concentrations of prodrug BMS-986231, its byproduct BMT-284730 and other metabolites (eg, BMT-279554 & CAR-000463) and change-from-baseline QTcF (Δ QTcF) with the intent to exclude an effect > 10 msec at clinically relevant plasma levels.

In addition, the effect of BMS-986231 on the placebo-corrected Δ QTcF ($\Delta\Delta$ QTcF) will be evaluated at each post-dosing time point ('by-time point' analysis) using the Intersection Union Test. An analysis of categorical outliers will be performed for changes in heart rate (HR), PR, QRS, QTcF, T-wave morphology and U-wave presence

Pharmacokinetic Analyses

[figure not shown]
Blood samples will be collected from all subjects at 0.75, 4, 8, 14, and 48 hours during infusion and 4 hours after end of infusion and plasma concentrations will be measured using LC-MS. Pharmacokinetic parameters for BMS-986231 and BMT-284730 and other metabolites (eg, BMT-279554 & CAR-000463) will be estimated as appropriate. The plasma concentration may also be used to conduct population pharmacokinetic analysis and exposure-response analysis with select efficacy and safety endpoints. Results of the population pharmacokinetic and exposure-response analysis will be reported in a separate report.

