Central Laboratory Assessments			See Section 5.3.5.2 for Analytes
Hematology and Serum Chemistry		X	
Hs Troponin T		X	
NT-proBNP, Serum Cystatin C, NGAL		X	
CRP		X	
Urinalysis		X	
Urine creatinine, Na+, and K+		X	
Efficacy Assessments			
Resting Dyspnea measured by the Numerical Rating Scale (NRS) ^a		X	
Other Assessments			
Sensory Motor Survey		X	

^a If subject is receiving supplemental oxygen, perform NRS without removing oxygen

Table 5.1-2: Treatment and In-Hospital Follow-up (CV013011)

Procedure	Hour 0-23 ^a (Post Rand, Day 1)	Hour 24 ± 2	Hour 48 ± 2	Hour 72 ± 2	Hour 96 ± 2	Hour 120 ± 2 or Discharge ^{b c}	Notes (Time is relative to start of dosing)
Randomize Subject	X						Randomization must take place before Hour 0
Administer Study Medication		X					48 hour continuous infusion *Study medication infusion begin promptly after randomization*
Safety Assessments							
Body Weight		X	X	X	X	X	
Vital Signs: Blood Pressure and Heart Rate ^d	X	X	X	X	X	X	Perform Semi-Recumbent (at a 30° angle) Day 1: Hours 0, 0.25 (15 min), 0.5 (30 min), 0.75 (45 min), 1, 1.5, 2, 4, 5* , 6, 8, 9* , 10, 12, 14, 16, 18, 20, 22 Hours: 24, 28, 32, 36, 40, 44 Hours 48, 54, 60, 66 Hour 72 Hour 96 Hour 120 Perform measurements before IV bag change, when possible. Repeats as per Section 5.3.1 Perform also if signs or symptoms of hypotension *Part I (Cohort 1) only
Respiratory Rate	X	X	X	X	X	X	Day 1: Hours 6 and 12
Use of Oxygen Supplementation,	X	X	X	X	X	X	Day 1: Hours 6 and 12

Table 5.1-2: Treatment and In-Hospital Follow-up (CV013011)

Procedure	Hour 0-23 ^a (Post Rand, Day 1)	Hour 24 ± 2	Hour 48 ± 2	Hour 72 ± 2	Hour 96 ± 2	Hour 120 ± 2 or Discharge ^{b c}	Notes (Time is relative to start of dosing)
Oxygen Saturation							
Temperature		X	X	X	X	X	
12-Lead ECG		X	X	X		X	
Telemetry Monitoring	X						Continuous monitoring through Hour 50

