Holter Monitoring (Part II Cohort 2 Only)	X						For participating sites. Continuous monitoring through Hour 52. 12-lead ECGs will be extracted at 3 timepoints prior to the start of the infusion and at the same timepoints as PK determinations up to and including 48 hours post-dose (See section 5.5) Subjects will be supinely resting in a semi-recumbent position for at least 10 minutes prior to and 5 minutes after each timepoint for ECG extraction (Day 1: Hour 0.75, 4*, 8*, 14, 48 and Hour 52). When ECG extractions coincide with 12-lead safety ECGs, blood draws and other assessments, ECG extractions should, when feasible, be performed in said order.
Investigator Assessment of Signs of Congestion		X	X	X	X	X	Physical exam to assess signs and symptoms of congestion will include symptom assessments (dyspnea on exertion, dyspnea at rest, orthopnea, paroxysmal nocturnal dyspnea,

Table 5.1-2: Treatment and In-Hospital Follow-up (CV013011)

Procedure	Hour 0-23 ^a (Post Rand, Day 1)	Hour 24 ± 2	Hour 48 ± 2	Hour 72 ± 2	Hour 96 ± 2	Hour 120 ± 2 or Discharge ^{b c}	Notes (Time is relative to start of dosing)
							persistent coughing or wheezing, fatigue, and abdominal discomfort), and signs assessment (peripheral edema, pulmonary rales, tachypnea and/or oxygen desaturation, increased jugular venous pressure, hepatomegaly, ascites).
Assessment of Hypotension	X	X	X				Assessment of signs and symptoms of hypotension.
Serious Adverse Event Assessment				X			
Adverse Events Assessment				X			From Hour 0 to Hour 120. If subject is discharged before Hour 120, site asked to contact subject at Hour 120 for final AE collection
Concomitant Medications				X			
Local Laboratory Assessments							
Cumulative Urinary Output (Volume)		X	X	X	X	X	Provide daily volume
Pregnancy Test				X		X	WOCBP only
Central Laboratory Assessments							See Section 5.3.5.2 for Analytes
Hematology and Serum Chemistry		X	X	X		X	
Hs Troponin T		X	X	X		X	
NT-proBNP, Serum Cystatin C, NGAL		X	X	X		X	

Table 5.1-2: Treatment and In-Hospital Follow-up (CV013011)

Procedure	Hour 0-23 ^a (Post Rand, Day 1)	Hour 24 ± 2	Hour 48 ± 2	Hour 72 ± 2	Hour 96 ± 2	Hour 120 ± 2 or Discharge ^{b c}	Notes (Time is relative to start of dosing)
CRP			X			X	
Urinalysis				X			
Urine creatinine, Na+ and K+		X	X	X		X	
Pharmacokinetics							See Section 5.5

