Pharmacokinetic Blood Samples Collection and Preparation of Blood Samples	X		X	X			Part I Cohort 1: Day 1: Hour 0.75, 4, 8, 14 Hour 48 Hour 52 Part II Cohort 2: Day 1: Hour 0.75, 6, 14 Hour 48 Hour 52 Perform measurements before IV bag change or stopping the infusion, whenever possible. Collect sample when dose lowered due to a safety event and also at time of early discontinuation of study drug.

Table 5.1-2: Treatment and In-Hospital Follow-up (CV013011)

Procedure	Hour 0-23 ^a (Post Rand, Day 1)	Hour 24 ± 2	Hour 48 ± 2	Hour 72 ± 2	Hour 96 ± 2	Hour 120 ± 2 or Discharge ^{b c}	Notes (Time is relative to start of dosing)
Efficacy Assessments							
Resting Dyspnea measured by Numerical Rating Scale (NRS) ^e	X	X	X	X		X	Day 1: Hours 6 and 12
Resting Dyspnea measured by 7-point Likert Scale ^e	X	X	X	X		X	Day 1: Hours 6 and 12
Patient Global Assessment measured by 7-point Likert Scale ^e	X	X	X	X		X	Day 1: Hours 6 and 12
Assessments of Worsening Heart Failure		X	X	X	X	X	Documentation of Worsening Physical Signs and Symptoms of Heart Failure, and Documentation of Initiation or Increased dose of Parenteral Diuretic, Vasodilator and/or Inotropes, or Need for Mechanical interventions (mechanical ventilation, circulatory support, ultrafiltration or dialysis). Assessments to cover prior 24 hour period.
Wristworn Actigraphy monitoring device (watch) (Part II Cohort 2)			X	X	X	X	For participating sites. Provide the device to subjects at the end of the 48 hours infusion or when the study drug has been permanently discontinued
Other Assessments							
Sensory Motor Survey						X	

^a Hour 0 defined as start of study medication infusion

- b Visit to occur at Hour 120 \pm 2 or Discharge, whichever comes first. If subject is discharged after Hour 120, no further protocol in-hospital visits are completed
- c Assessments required at Discharge Visit should not be repeated if performed within previous 12 hours
- d Vital signs should be taken within (\pm 0.25)
- e If subject is receiving supplemental oxygen, perform NRS without removing oxygen

Table 5.1-3: Outpatient Follow-up (CV013011)

[figure not shown]
Procedure	Day 32 (± 2 Days) Clinic Visit ^a	Day 182 (± 5 Days) Phone Visit ^b	Notes
Safety Assessments			
Vital Signs: Blood Pressure and Heart Rate	X		When possible, perform Semi-Recumbent (at a 30° angle)
Respiratory Rate	X		
Body Weight	X		
Temperature	X		
Serious Adverse Events Assessment	X		
Local Laboratory Assessments			

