5.3.7 Holter Recordings

Holter monitoring with extraction of serial ECGs will be performed in a sub-set of 51 patients in Part II Cohort 2 only, randomized 1:1:1 to placebo and the two active doses in Part II Cohort 2 of the study. The 12-lead Holter and ECG equipment will be supplied and supported by the sponsor and a core electrocardiographic laboratory. ECGs to be used in the analyses will be selected by pre-determined time points as defined in the Table of Assessments, and will be read centrally by a core electrocardiographic laboratory. The analysis will be described in detail in a separate analysis plan.

Ten 14-second digital 12-lead ECG tracings will be extracted from the continuous Holter recordings using the 'TQT Plus method', a computer-assisted and statistical process utilized by a core electrocardiographic laboratory.

At each protocol-specified timepoint, 10 ECG replicates will be extracted from a 5-minute “ECG window” (typically, the last 5 minutes of the 15-minute period when the subject is maintained in a supine or semi-recumbent quiet position. Subjects must be instructed to rest in a quiet position 15 minutes before each PK draw.

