5.5 Pharmacokinetic Assessments

[figure not shown]
Blood samples will be collected for pharmacokinetic assessments as described in Table 5.5-1.

Table 5.5-1: Pharmacokinetic Assessments

Time Relative to Dosing Hour (window)	Time (Relative to Dosing) Hour: Min	PK Blood Sample
0.75 (\pm 0.25)	00:45	X
4 (\pm 0.5)	04:00	X
8 (\pm 0.5)	8:00	X
14 (\pm 4)	14:00	X
48 (\pm 1)	48:00	X
52 (\pm 1)	52:00	X
Dose lowered due to safety event (\pm 0.5)	Misc.	X
Early Discontinuation	Misc.	X

Collect the 4 and 8 hour PK samples immediately prior to the IV bag change whenever possible. In addition, collect a PK sample from the subject when the dose is lowered due to a safety event and also at time of early discontinuation of study drug. The sample should be collected immediately before or after the decision to change the dose was made.

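### In Part II the Holter ECG times and the PK sampling times disagree, so on the times listed in Table 5.1-2 the Hour 6 concentration has no ECG for the QTcF exposure-response analysis

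*Protocol*

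**What the plan says.** All of this text is in the current protocol version (02c); the two Table 5.1-2 rows read the same in Revised Protocol 02.

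- **Table 5.1-2, Holter row (Part II only).** ECGs are extracted "at the same timepoints as PK determinations up to and including 48 hours post-dose", with a pointer to Section 5.5. The next sentence, on resting position, refers to "each timepoint for ECG extraction (Day 1: Hour 0.75, 4*, 8*, 14, 48 and Hour 52".
- **Table 5.1-2, PK row.** "Part II Cohort 2: Day 1: Hour 0.75, 6, 14 Hour 48 Hour 52". The same row assigns Hours 4 and 8 to Part I.
- **Table 5.1-2, vital-signs row.** This holds the only asterisk key in the table: "Part I (Cohort 1) only".
- **Section 5.5, Table 5.5-1.** Draws are at 0.75, 4, 8, 14, 48 and 52 h, with no split by part and no row for Hour 6. The text adds: "Collect the 4 and 8 hour PK samples immediately prior to the IV bag change whenever possible".
- **Section 8.4.4.** All subjects are sampled at 0.75, 4, 8, 14 and 48 h and 4 h after the infusion ends. SAP Section 7.8 says the same, but SAP Section 2.4 bases the SAP on Revised Protocol 01, before Holter monitoring was added.
- **Section 5.3.7.** There are 51 Holter subjects, allocated 1:1:1. "ECGs to be used in the analyses will be selected by pre-determined time points as defined in the Table of Assessments".
- **Synopsis, Cardiodynamic ECG assessment.** Change in QTcF is modelled on plasma concentration "with the intent to exclude an effect > 10 msec at clinically relevant plasma levels".

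**The concern.** An exposure-response model of QTcF needs each concentration to have an ECG taken at about the same time. Section 5.3.7 selects the analysed ECGs by the times in the assessment table, so the hours listed there have operational force. Read as listed, the core laboratory extracts at 4 and 8 h, when Part II has no scheduled draw, and not at 6 h, when it does. The model then loses its only scheduled Part II pairing between the first hour of infusion and Hour 14.

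A second consequence reaches beyond the Holter subset. A site could draw Part II blood at 6 h, or at 4 and 8 h, depending on which table it follows, and Hour 6 has no collection window anywhere.

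**Working it through.** No sample size or power figure is involved; the check compares the listed times as sets.

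**Inputs**
- Listed ECG times (Holter row): E = {0.75, 4, 8, 14, 48, 52}
- Part II PK times (PK row): P = {0.75, 6, 14, 48, 52}
- Table 5.5-1 PK times: T = {0.75, 4, 8, 14, 48, 52}, with windows of ±0.5 h at 4 h and at 8 h
- Active-arm Holter subjects: 51 × 2/3 = 34. Placebo subjects contribute no drug concentrations.

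**Matched times.** E and P share {0.75, 14, 48, 52}. PK without ECG: {6}. ECG without PK: {4, 8}.

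**Active-arm pairs under each reading, assuming complete sampling**

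| Reading | PK times without an ECG | ECG times without PK | Pairs / scheduled samples |
|---|---|---|---|
| 1. Listed hours as they stand | 6 h | 4 h, 8 h | 34 × 4 = 136 of 34 × 5 = 170 (80%) |
| 1a. Same, through Hour 48 only | 6 h | 4 h, 8 h | 34 × 3 = 102 of 34 × 4 = 136 (75%) |
| 2. Asterisk means Part I only | 6 h | none | 136 of 170 (80%) |
| 3. Table 5.5-1 governs Part II draws | none | none | 34 × 6 = 204 of 204 |
| 4. Same-times rule overrides the listed hours, through Hour 48 | none | none | 34 × 4 = 136 of 136 |

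Each reading contradicts some of the text:
- Reading 1 breaks the rule that ECG times follow PK times.
- Reading 2 applies a Part I label inside a Part II-only procedure, and Hour 6 is still unpaired.
- Reading 3 makes the Part II PK row wrong.
- Reading 4 makes the listed ECG hours wrong.

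Hour 52 is a separate conflict: the extraction rule stops at 48 h, but the list includes Hour 52.

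**Hour 6 against the Table 5.5-1 windows.** The 4 h window ends at 4 + 0.5 = 4.5 h and the 8 h window starts at 8 − 0.5 = 7.5 h. Hour 6 is 1.5 h from each. The 14 h window (±4 h) starts at 10 h. No window covers Hour 6.

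**Gap between matched pairs, readings 1 and 2.** 14 − 0.75 = 13.25 h nominally. With the Table 5.5-1 windows (0.75 ± 0.25 and 14 ± 4) it runs from 10 − 1.0 = 9 h to 18 − 0.5 = 17.5 h.

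**After adding an Hour 6 ECG to the Part II PK row's times, with Hour 52 extracted.** 34 × 5 = 170 of 170 scheduled samples are paired.

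**The case against.** The strongest reply is that the Holter row's only direct statement of which ECGs to extract is the same-times rule. The hour list is a parenthesis in a sentence about resting position. Combined with the Part II PK row, the rule already calls for an Hour 6 ECG. That is reading 4, and it is a fair one. It does not remove the problem, because Section 5.3.7 sends the core laboratory to the table's time points and the only explicit ECG hours there are the wrong ones for that reading. The rule also points to Section 5.5, which has no Hour 6.

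Other objections carry some weight:

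- The document history says Administrative Letter 04 (August 2018) revised the PK schedule for Part II. The letter is not supplied. It predates version 02c (September 2019), where the conflict remains.
- The Holter analysis has its own plan, also not supplied, which may define the pairing. It could settle the analysis, but it would not make the site-facing tables agree on when to draw blood.
- The recording is continuous through Hour 52 and Section 5.3.7 says "Subjects must be instructed to rest in a quiet position 15 minutes before each PK draw", so an Hour 6 ECG can be recovered later. This stands, and it makes the correction cheap.
- No loss of precision for the 10 msec exclusion has been calculated. Pairs remain at 0.75, 14, 48 and 52 h on the plain list. The claim is therefore about missing pairs and an unresolved schedule, not a demonstrated failure of the analysis.
- Samples taken at dose lowering or early discontinuation have no listed ECG under any reading. The counts cover scheduled samples only.
- SAP Section 7.8 reflects version lag and adds little on its own.

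**Conclusion.** The concern holds. Protocol version 02c contradicts itself on Part II ECG and PK times, and none of the four readings reconciles the text. If the hours listed in Table 5.1-2 are followed, 34 of 170 scheduled active-arm concentrations (34 of 136 through Hour 48) have no ECG, and the nominal gap between pairs is 13.25 h. This is so whichever way the asterisks are read. The counts assume exactly 34 active-arm Holter subjects and complete sampling. They do not apply if Table 5.5-1 or the same-times rule is taken to govern.

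The scope is limited to an optional sub-study of 51 subjects, with no effect on the primary or secondary endpoints. ECGs at 4 and 8 h would still serve the by-time-point and outlier analyses. The uncertainty over draw times (6 h, or 4 and 8 h) does extend to every Part II subject sampled. The text should be corrected, but the point does not threaten the trial's main conclusions.

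**What to change.** Reconcile the Holter row, the Part II PK row, Table 5.5-1 and Section 8.4.4 of the protocol, and SAP Section 7.8, to a single Part II schedule. In doing so:

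- define the asterisks on Hours 4 and 8, or remove them;
- give a collection window for every scheduled Part II PK time;
- state whether an ECG is extracted at Hour 52;
- if the Hour 6 draw stands, add an Hour 6 extraction so that every scheduled Part II sample is paired, keeping Hours 4 and 8 for the by-time-point and outlier analyses if wanted;
- say how samples taken at dose lowering or early discontinuation enter the exposure-response model, since they have no listed ECG.

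The cost is a clarification to the protocol tables and SAP and an instruction to the core laboratory. If the Hour 6 draw stands, no additional blood draw or recording is needed, because the Holter already runs through Hour 52 and rest before each PK draw is already required.

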The primary endpoint of the study is the incidence of clinically relevant hypotension, defined by SBP < 90 mm Hg (confirmed by a repeated value < 90 mm Hg) or symptoms of hypotension, up to 6 hours after the end of study drug infusion. Thus hypotension will be assessed by collection of symptoms and blood pressure measurements.

Symptomatic hypotension is defined as the presence of both low SBP and symptoms (eg, lightheadedness, dizziness, etc.) due to low blood pressure.

Blood pressure measurements should be performed with the subject in a semi-recumbent (about a 30° angle) position, whenever possible.

Blood pressure will be measured as indicated in [Table 5.1-2](#) within (± 5 min in the first hour then ± 0.25 (15 min)) of the specified time points. In addition, sites may perform measurements at intervals defined by institutional standard of care for subjects receiving vasodilators, but no less than what is described in [Table 5.1-2](#).

If the study drug dose is modified (decreased, interrupted, resumed or discontinued), the frequency of blood pressure measurements will follow a more intensive schedule for up to 6 hours following the dose modification (see table below). Upon completion of the intensive schedule, measurements can be either resumed per the original schedule, or follow the discontinuation schedule if the drug is permanently discontinued.

Schedule of Blood Pressure Collection Following a Dose Modification

	30 minutes Post	1 hour post	2 hours post	4 hours post	6 hours post
Dose reduction	X	X	X	X	X
Dose interruption	X	X	X	X	
Dose resumption	X	X	X	X	X
Dose discontinuation	X	X	X	X	X

Details for management of low blood pressure are detailed in [section 5.3.1](#)

In addition to assessments of blood pressure, the Investigator will be asked to collect and assess signs and symptoms of low blood pressure.

Efficacy Outcome Measures: Efficacy assessments will include the following:

Patient assessments of dyspnea severity at rest as measured by the 11-point Numerical Rating Scale (NRS) scores at screening and at 0, 6, 12, 24, 48, 72, and 120 hours after the start of study drug infusion.

Patient assessments of dyspnea severity at rest, using the 7-point Likert scale at 6, 12, 24, 48, 72, and 120 hours after the start of study drug infusion.

Patient assessments of global clinical status using the 7-point Likert scale at 6, 12, 24, 48, 72, and 120 hours after the start of study drug infusion.

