5 STUDY ASSESSMENTS AND PROCEDURES

5.1 Flow Chart/Time and Events Schedule

Table 5.1-1: Screening Procedural Outline (CV013011)

Procedure	Screening Visit (-18 for Part I Cohort 1 or -48 for Part II Cohort 2, up to 0 hours)	Pre- Randomization Procedures	Notes
Eligibility Assessments			
Informed Consent	X		
Review Inclusion/Exclusion Criteria	X	X	
Medical History	X		
Confirm administration of IV diuretic and time of administration	X		
Safety Assessments			
Complete Physical Examination	X		
Body Weight	X		
Height	X		
Vital Signs: Blood Pressure and Heart Rate	X	X*	Perform Semi-Recumbent (at a 30° angle). *Within 15 minutes prior to randomization
Respiratory Rate	X	X	
Use of Oxygen Supplementation, Oxygen Saturation	X	X	
Temperature	X	X*	*Within 15 minutes prior to randomization
Chest X-ray	X		As applicable, refer to section 3.3.1 X-ray obtained for the current episode of ADHF as part of standard of care may be used.

Table 5.1-1: Screening Procedural Outline (CV013011)

Procedure	Screening Visit (-18 for Part I Cohort 1 or -48 for Part II Cohort 2, up to 0 hours)	Pre- Randomization Procedures	Notes
12-Lead ECG (Electrocardiogram)	X		
Telemetry Monitoring		X	Begin within 2 hours prior to start of study medication infusion
Holter Monitoring (Part II Cohort 2 Only)		X	For participating sites. Begin within 2 hours prior to start of study medication infusion
Investigator Assessment of Congestion		X	Physical exam to assess signs and symptoms of congestion will include symptom assessments (dyspnea on exertion, dyspnea at rest, orthopnea, paroxysmal nocturnal dyspnea, persistent coughing or wheezing, fatigue, and abdominal discomfort), and signs assessment (peripheral edema, pulmonary rales, tachypnea and/or oxygen desaturation, increased jugular venous pressure, hepatomegaly, ascites).
Serious Adverse Events Assessment	X	X	Begins at time subject signs ICF
Review concomitant medications/procedures	X	X	
Local Laboratory Assessments			See Section 5.3.5.1 for Analytes
Hematology and Serum Chemistry	X		
eGFR	X		
Trough Serum Digoxin	X		If receiving digitalis glycosides
Hs Troponin T	X		
Coagulation Tests	X		Prothrombin Time (PT or PT-INR)
NT-proBNP or BNP	X		As per site preference

Table 5.1-1: Screening Procedural Outline (CV013011)

Procedure	Screening Visit (-18 for Part I Cohort 1 or -48 for Part II Cohort 2, up to 0 hours)	Pre- Randomization Procedures	Notes
Pregnancy Test	X		

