4.1.2 Secondary Efficacy Endpoints

Secondary endpoints include the following:

- Change in NT-proBNP from baseline to Hour 24, 48, 72, 120 or discharge (whichever comes first), and at Day 32
- Change in patient-reported resting dyspnea from baseline through Hour 72, as measured by the area under the curve (AUC) of the 11-point Numerical Rating Scale (NRS) obtained at baseline, and Hours 6, 12, 24, 48, and 72

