8.2 Baseline Measurements

For analyses involving baseline, the baseline value is defined by the last value prior to the start of infusion, unless otherwise noted.

When there is a missing baseline assessment it will not be imputed, thus, subjects are excluded from any changes from baseline analysis for which they have a missing baseline value.

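### The site schedule omits the Hour 0 dyspnea NRS that the synopsis lists; the only tabled pre-dose score is an untimed pre-randomization one, which the SAP's NRS baseline window, read literally, does not admit

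*Protocol*

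**What the plan says.** **Synopsis (Efficacy Outcome Measures).** NRS dyspnea is to be collected as "scores at screening and at 0, 6, 12, 24, 48, 72, and 120 hours after the start of study drug infusion". The two Likert assessments listed next to it start at Hour 6.

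**Protocol Table 5.1-1.** The row "Resting Dyspnea measured by the Numerical Rating Scale (NRS") is marked in the pre-randomization column only. Its one footnote concerns supplemental oxygen. Blood pressure, heart rate and temperature in the same column carry the limit "Within 15 minutes prior to randomization"; the NRS carries none.

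**Protocol Table 5.1-2.** The row "Resting Dyspnea measured by Numerical Rating Scale (NRS") is marked in the Hour 0–23 column, with the note "Day 1: Hours 6 and 12". The vital-signs row of the same table names Hour 0 explicitly: "Day 1: Hours 0, 0.25 (15 min), 0.5 (30 min), 0.75 (45 min), 1, 1.5, 2, 4". The NRS and vital-signs rows treat Hour 0 in the same way in Revised Protocol 02 and 02c.

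**Endpoint.** Protocol 8.3.2 and SAP 4.1.2 define the change in NRS AUC through Hour 72 from scores "obtained at baseline, and Hours 6, 12, 24, 48, and 72".

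**Baseline rules.** Protocol 8.4 and SAP 8.2 take the last value before infusion as baseline, unless otherwise noted. SAP Table 8.3-1, which covers the NRS, sets the baseline range from randomization to Hour 0. SAP 8.2 does not impute a missing baseline: "subjects are excluded from any changes from baseline analysis for which they have a missing baseline value".

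**The concern.** In this endpoint the baseline score is both the value subtracted and a model covariate. It should describe dyspnea as the infusion starts. The site tables provide instead a score taken at an unstated time before randomization. Randomization, drug preparation and ongoing diuretic treatment can all fall between that score and Hour 0. The protocol asks for a prompt start but sets no maximum delay.

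Two things are at stake. First, an older score can carry improvement that occurred before any study drug, and it may predict later scores less well. Second, the SAP's NRS window opens at randomization, and the site tables schedule no NRS between randomization and Hour 0. Whether subjects assessed on schedule have a usable baseline then depends on how a programmer reads two SAP rules together.

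**Working it through.** The plan states no figure on this point, so there is none to reproduce. The check compares the schedules, then looks at what an older baseline does to the AUC.

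**1. Pre-dose NRS by source**

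| Source | Pre-dose NRS |
|---|---|
| Synopsis | Screening and Hour 0 |
| Table 5.1-1 | Pre-randomization column, no time limit |
| Table 5.1-2 | None (Day 1 starts at Hour 6) |
| Section 5.7.1.1 | No times given |
| SAP Table 8.3-1 | Accepted from randomization to Hour 0 |

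The omission is hard to read as implied, because the vital-signs row writes Hour 0 out. The synopsis gives the NRS an Hour 0 and the Likert scales none, yet Table 5.1-2 gives all three rows the same Day 1 note. The likely explanation is that the NRS row lost its Hour 0 in drafting; that is an inference.

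**2. Age of the score.** Randomization must precede Hour 0 (Table 5.1-2). Drug is prepared at randomization (Section 4.1), and Section 4.3 foresees dosing more than 1 hour after reconstitution. The only outer limit is treatment within 18 hours (Part I) or 48 hours (Part II) of the first IV diuretic (Section 3.3.1).

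**3. Effect on within-arm ΔAUC.** Trapezoid: ΔAUC = Σ (t₍ᵢ₊₁₎ − tᵢ)(y₍ᵢ₊₁₎ + yᵢ)/2.
- At 0, 6, 12, 24, 48 and 72 h the weights are 3, 6, 9, 18, 24 and 12 (sum 72).
- Change at time zero is 0 by construction, so the weights that count sum to 72 − 3 = 69.
- A baseline 1 point too high for everyone (assumed) therefore moves within-arm ΔAUC by −69 point-hours.
- SAP 7.5.2 models only Hours 24, 48 and 72, with three trapezoids. Taking the first time as 0, the weights are 12, 24, 24 and 12, and the shift is −(72 − 12) = −60. That the SAP model omits Hours 6 and 12 is a separate matter.

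**4. Effect on the comparison between arms.** A simulation used values that are not in the documents: 70 per arm, baseline SD 2, residual SD 1.5 per visit, a true effect of −0.5 point at each visit (AUC difference −0.5 × 69 = −34.5), and baseline-adjusted regression on each subject's AUC.

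| Baseline error | Mean estimated difference | Empirical SE |
|---|---|---|
| None | −34.4 | 8.7 |
| +1 point | −34.3 | 8.6 |
| +1 point, noise SD 1 | −34.4 | 10.7 |
| +1 point, noise SD 2 | −34.5 | 12.9 |

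The estimate stays on target; only its precision changes.

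**5. Precision by formula.** Residual variance is proportional to 1 − r², where r is the correlation of baseline with later scores. The documents give no r. Starting from an assumed 0.6 (1 − 0.36 = 0.64):

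| r falls to | 1 − r² | Ratio to 0.64 | Equivalent loss of subjects |
|---|---|---|---|
| 0.55 | 0.6975 | 1.09 | 8% |
| 0.50 | 0.75 | 1.17 | 15% |
| 0.40 | 0.84 | 1.31 | 24% |

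**6. SAP rules together.** A subject scored before randomization and next at Hour 6 has no NRS inside the Table 8.3-1 baseline range. If that table governs, the baseline is missing and SAP 8.2 removes the subject from the change analysis.

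**The case against.** The strongest reply is that baseline is already defined as the last value before infusion, and the pre-randomization score meets that definition. This stands under the protocol. A reader might infer that the AUC has no starting value and cannot be computed; the protocol rule, and a change of 0 at time zero by construction, show otherwise.

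A reader might also infer that the NRS analysis would lose every subject assessed on schedule. That follows only if Table 8.3-1 overrides the general rule, and there is good reason to think the window is generic wording. SAP Tables 8.3-2 to 8.3-4 use the same range for laboratory tests, ECG, respiratory rate and temperature. In the site tables the central laboratory samples, respiratory rate and temperature are last taken before randomization, and the 12-lead safety ECG is marked at screening only. Read literally, the window would remove those baselines too, including NT-proBNP, the other secondary endpoint. Table 8.3-1 even gives a baseline row to a Likert scale that asks about change since study drug started. The objection does not fully dispose of the problem, because the general rule yields to anything otherwise noted and Table 8.3-1 can be read as such a note.

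Three smaller points have weight. The SAP is based on Revised Protocol 01, whose tables are not in the documents, so whether it fitted its own schedule cannot be checked. The synopsis screening score may be the one in Table 5.1-1, whose title concerns screening; the clear omission is Hour 0. And nothing in the documents shows that gaps before infusion were long.

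**Conclusion.** The contradiction is real and should be reconciled. The synopsis calls for an Hour 0 NRS, Table 5.1-2 does not schedule it, and the remaining pre-dose score has no time limit.

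The consequences are limited. The score precedes randomization in a double-blind trial, so its error is unrelated to arm and the between-arm comparison is unbiased. Within-arm ΔAUC, which SAP 7.5.2 estimates, may include pre-drug improvement: 69 point-hours for each point of baseline excess on the endpoint's time points, or 60 on the SAP's. Some precision may be lost, but the amount cannot be derived from the documents. A reader might settle on a 15% loss, about 10 of 70 per arm; that rests on one assumed pair of correlations. A fall from 0.6 to 0.58 gives 1 − 0.64/0.6636, about 3.6%.

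Exclusion of subjects assessed on schedule is what the SAP text says if read literally, but probably not what it intends. The endpoint is secondary and SAP 7.1 plans no significance testing, so this does not threaten the trial's primary conclusion. It merits correction because the remedy is nearly free and already in the synopsis.

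**What to change.** 1. In Table 5.1-2, change the NRS note to read Day 1: Hour 0 (before the start of infusion), Hours 6 and 12. This matches the synopsis.
2. In SAP Table 8.3-1, make the NRS baseline the last score before infusion starts, and accept the pre-randomization score if Hour 0 is missed. The table edit alone is not enough, because the present window would not admit that fallback. For subjects already assessed under the existing tables, this is the change that matters.
3. Reconcile the same baseline range in SAP Tables 8.3-2 to 8.3-4 with the times at which those assessments are scheduled.

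The cost is one extra 0–10 question when staff already take Hour 0 vital signs, one table note, and a short SAP amendment. No dose or clinical rule is affected.
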